3 STUDY DESIGN

This is a mixed-methods study comprised of 4 work packages, which address the above objectives. The study will span 24 months. A schematic of the design is included as an appendix to this document. We will describe work to be conducted in each WP in the sections below, however this is an iterative study and some details will not be determined until earlier WP's have been reported.

3.1 RESEARCH SETTING

For qualitative WPs (1b & 3) we will work with the CRN West Midlands and North West Coast to recruit patients and PCC from approximately 35 general practices and SCSs from a range secondary care trusts. The sites must be actively engaging in the A&G process. The same types of activity will be taking place at each site in terms of identifying and recruiting patients and clinicians. Participants will be interviewed once over the course of the study.

Quantitative WPs (1a, 2a &2b) will be conducted within the Clinical Practice Research Datalink (CPRD).

4 WORK PACKAGE 1A (QUANTITATIVE)

This section of the protocol relates to CPRD Protocol ID: 24_004022, approved by the Research Data Governance Secretariat on 11/06/2024.

Study Title: Trends over time in the use of Advice and Guidance and variation by sociodemographics and type of health condition: repeated cross-sectional and cohort study

4.1 OBJECTIVES, SPECIFIC AIMS & RATIONALE

The objective of this sub-study is to determine the extent of variation in use of Advice and Guidance (A&G) in primary care. The specific aims are to determine:

1) if use of A&G has increased over time in comparison to direct referrals

NIHR 158681BADGER			
Protocol Version 2.0 18/06/2024	CPMS: 58336	IRAS No: 333799	CPRD ID: 24_004022

- 2) variation in use of A&G by socio-demographic characteristics
- 3) which specialties and health conditions have higher rates of A&G
- 4) the percentage of A&G which end up with a direct referral.

This study is the first part of a programme of work which has the overall aim to understand whether A&G reduces waiting times and access to specialist care as planned, without making the quality of patient care worse. This initial study will examine changes in use of A&G over time and how it varies by sociodemographic characteristics and specialty.

4.2 STUDY DETAILS

4.2.1 Study type

Descriptive and exploratory / hypothesis generating

4.2.2 Study design

Repeated cross-sectional and cohort

4.2.3 Feasibility counts

A feasibility count between 2015 and 2023 indicates approximately 1.7million A&G requests for 975,000 individuals.

4.2.4 Outcomes to be measured

Advice and Guidance requests

Direct referrals to specialties

4.2.5 Sample size considerations

The feasibility count of 975,000 individuals gives an estimated mean of 108,000 per annum over the nine years of the study. Assuming an annual denominator population of 14 million (and hence prevalence of A&G of approximately 800/100,000), then per annum 95% confidence limits for the prevalence of A&G will be \pm 5/100,000. For assessing percentage of A&Gs which result in a referral, assuming an estimate of 50%, then per annum 95% confidence limits will be \pm 0.3% overall and \pm 3% for a lowest covariate (e.g., ethnicity group) category prevalence of 1%.

4.2.6 Planned use of linked data and benefit to patients in England

Patient level Index of Multiple Deprivation (IMD) data will be used in order to assess extent of variation and potential inequality in use of A&G by deprivation. If Patient level IMD is missing, we will include a 'not recorded' category.

Use of the CPRD Aurum Ethnicity Record has shown to yield representative distributions across ethnic categories compared to national data on the UK population and a smaller proportion classified as 'other'.²¹ Use of the CPRD ethnicity records will:

- 1) allow us to access an immediate source of ethnicity with clear and consistent allocation of an ethnicity category that has already been derived for each individual,
- 2) reduce extent of missing data on ethnicity,
- 3) use ethnic groupings returned from an externally developed and validated algorithm,
- 4) allow consistency and hence greater comparability with other studies using CPRD,

NIHR 158681BADGER			
Protocol Version 2.0 18/06/2024	CPMS: 58336	IRAS No: 333799	CPRD ID: 24_004022

5) allow finer definitions of ethnicity (within Asian, black, mixed/multiple, white, other groups), hence more opportunity to detect inequalities across ethnic groups, rather than just comparing white versus non-white.

CCG pseudonym is requested to explore extent of variation in A&G use across healthcare localities in order to identify potential inequities in practice.

The use of linked data will be beneficial to patients in England by determining whether the use of A&G versus usual referral varies by key socio-demographic factors, e.g. patient-level deprivation, or locality, e.g. by CCG pseudonym, only available through linkage.

The outputs of this research may serve as reassurance to A&G users of its benefits to support primary care and specialist services work together effectively and safeguard quality of care for patients in a pressured healthcare environment. We may, however, identify inequity in practice that will be fed back into the wider programme of research to develop evidence-to-practice recommendations.

4.2.7 Definition of the study population

All individuals in the CPRD Aurum database, regardless of age, with an A&G or referral recorded between 01/01/2015 to date of the most recent Aurum build (currently March 2024). For determination of incident A&G, they must have 24 months prior registration in CPRD Aurum or be aged 2 years or under. There is no comparison or control group.

4.2.8 Exposures, outcomes and covariates

1) Advice & Guidance

We will determine coded A&G events and, where possible, the specialty linked to the A&G. When a Choose and Book referral is made through e-RS (by selecting either the satellite button for "advice and guidance" which equates to an A&G request or the "Refer/Advice" satellite button which equates to the standard or direct referral to secondary care), the referral must be saved before the activity can be completed and exited back to the clinical software system. To save the activity, a code must be entered to then move back into another part of the healthcare record. For A&G requests, the coded term is "Advice and guidance requested." We will also include in our codelist the code "Advice and guidance received" which we will use to indicate A&G if the patient does not have an "Advice and guidance requested" code within the same study time period. We will map A&G to specialty (e.g. rheumatology, neurology) and type of health condition (e.g. musculoskeletal, cardiovascular). Given A&G coded events may not routinely have the specialty recorded we will use information from direct referrals (sampled from 3 specified years - 2015, 2019, 2023 - within our study period) as the basis for mapping to specialty. We will first determine morbidity/symptom codes recorded on the date of all direct referrals (defined below) with a named specialty, or in the prior 2 weeks. We will determine which Read or SNOMED CT codes are most frequently recorded with referral to each specialty and use these to map (impute) specialties in those with an A&G event based on matching these codes to Read/SNOMED CT morbidity or symptom codes recorded on the date of A&G or in the prior 2 weeks. Where the specialty is still unknown after this mapping exercise, we will review all codes in the 2 weeks prior to or on date of A&G request and agree on specialty (guided by Read code chapter) by consensus or define as unknown if no consensus. Type of health condition will be based on specialty or morbidity/symptom code at date of A&G event.

2) Direct referral

To derive the comparative prevalence and incidence of elective referrals, direct routine referrals will be determined using codes with a term indicating a referral and defined by consensus of study team to indicate a routine referral to a specialty (i.e. not fast track or referral with an intention to admit / emergency referral). To ascertain A&G events which result in a direct referral, we will determine

NIHR 158681BADGER			
Protocol Version 2.0 18/06/2024	CPMS: 58336	IRAS No: 333799	CPRD ID: 24_004022

referrals within 122 days (4 months) after date of an A&G request. These will be defined as i) a direct referral code defined as above and by ii) linking events in the Referrals table to the Observation table and determining duration of time between the linked observation event and the A&G request date. We will also determine referrals within 122 days (4 months) before an A&G request to see how often A&G requests follow a referral request. As a sensitivity analysis we will repeat for 365 days (12 months) either side of the A&G request date. Code lists for A&G have been derived and used in our CPRD feasibility study (FS_002830). The draft code list for direct referral has also been developed. These code lists are included in the appendix.

Covariates:

- 1) Age at date of A&G request (categorised)
- 2) Sex
- 3) Geographical region
- 4) CCG pseudonym
- 5) Ethnicity group
- 6) Deprivation (based on IMD quintiles)

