4.3 DATA / STATISTICAL ANALYSIS

We will determine the annual total number of A&G and total number of routine direct referrals from 2015 to 2023. Annual prevalence will then be defined as the total number of patients with i) an A&G and ii) a routine referral code recorded within each calendar year, divided by the total registered population at the start of each calendar year and expressed per 100,000 persons. Annual incidence will be defined (as in our previous incidence studies) as the total number of patients with i) A&G and ii) routine referral codes recorded within each calendar year who have no recorded A&G or routine referral codes in the previous 24 months, divided by the total registered population with at least 24 months registration at the start of each calendar year, and expressed per 100,000 persons. We will determine prevalence and incidence overall, and stratified by age and sex.

Patterns of A&G use (number, prevalence, incidence) will also be described across specialties and type of health condition, and by neighbourhood deprivation, ethnicity, CCG, and geographical region to assess if any change over time in consultation incidence and prevalence varies by these characteristics. We will produce caterpillar plots to show variation by geographical region and CCG. We will repeat for quarterly incidence and prevalence of A&G (up to date of most recent CPRD Aurum build). We will use joinpoint regression analysis and segmented regression on the annual and quarterly prevalence and incidence to determine impact of the COVID pandemic [2020/2021] and changes in policy on A&G.

Within those with A&G we will derive the percentage with a recorded referral in the 122 days (4 months) i) before and ii) after A&G record and compare these over time, and by the covariates (excluding those with less than four months of follow-up), descriptively and by using binary logistic regression. We will repeat for the sensitivity analysis of 12 months. We will descriptively compare trends in incidence and prevalence of A&G and routine direct referrals with publicly available data on trends on e-referrals from https://digital.nhs.uk/dashboards/ers-open-data which currently covers the period October 2019 to March 2024.

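### The rule for counting 'A&G received' codes uses an undefined study period instead of a time gap, so it double counts some A&Gs or drops others, depending on how it is read

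*Protocol*

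**What the plan says.** Protocol section 4.2.8 takes the 'requested' code as the main marker of an A&G. It admits the 'received' code as a fallback, "which we will use to indicate A&G if the patient does not have an" 'requested' "code within the same study time period". Nothing says how long that period is, and no number of days links a reply to a request.

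Three other places bear on the meaning:

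- Section 4.3 works by calendar year: "We will determine the annual total number of A&G and total number of routine direct referrals from 2015 to 2023". Prevalence counts patients with a code "recorded within each calendar year, divided by the total registered population at the start of each calendar year".
- Section 4.3 then adds a shorter unit: "We will repeat for quarterly incidence and prevalence of A&G (up to date of most recent CPRD Aurum build".
- Section 4.2.7 sets one long window, for people "with an A&G or referral recorded between 01/01/2015 to date of the most recent Aurum build (currently March 2024". Section 4.2.8 itself uses a similar term for the whole span from which 2015, 2019 and 2023 are sampled.

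For the link between an A&G and a later or earlier referral, section 4.2.8 does use day windows: 122 days, and 365 days as a sensitivity analysis. Section 5.2.8 takes the A&G definition over into WP2 by reference.

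**The concern.** A request and its reply are one A&G, separated by a lag. Whether a 'received' code is a duplicate depends on how long before it a request was made. It does not depend on whether the two dates fall in the same block of time. A rule based on blocks goes wrong at their edges if they are short, and across unrelated episodes if they are long.

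Annual and quarterly A&G counts and prevalence are main results of WP1a. The prevalence series go into the joinpoint and segmented regressions on the pandemic and on policy changes, and patterns of use are compared between regions and CCGs. In WP2 the first A&G or referral sets the exposure group and starts the clock for time to diagnosis. Two analysts who both follow section 4.2.8 faithfully could produce different series.

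**Working it through.** **The plan's own figure.** Section 4.2.5 gives 975,000 individuals over nine years and a denominator of 14 million. 975,000/9 = 108,333 per year, and 108,333/14,000,000 = 774 per 100,000, stated as about 800. The 95% half-width at 800 is 1.96 × √(0.008 × 0.992/14,000,000) = 4.7 per 100,000, which rounds to the stated ±5. This is correct. As a share of the prevalence it is 5/800 = 0.6%. It describes the sampling error of the annual figure only; no quarterly precision is stated.

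**Reading A: the period is the analysis year or quarter.** Take a request on the last day of a quarter with the reply coded a week later. The second quarter holds a 'received' code and no 'requested' code, so the A&G counts in both. With requests spread evenly, the share of coded replies that cross a boundary is lag ÷ period length. The protocol gives no lag, so the lags below are assumptions. The last two columns also assume that half of requests have a coded reply and that the patient has no other request in the new period.

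| Assumed lag | Crosses quarter (÷91.25) | Crosses year (÷365) | Extra A&Gs, quarter | Extra A&Gs, year |
|---|---|---|---|---|
| 5 days | 5.5% | 1.4% | 2.7% | 0.7% |
| 14 days | 15.3% | 3.8% | 7.7% | 1.9% |
| 28 days | 30.7% | 7.7% | 15.3% | 3.8% |

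A simulation dropped the assumption of no other request. It used 300,000 patients with a mean of 1.74 A&Gs each (1.7 million/975,000, section 4.2.3) at random dates over nine years. A 'requested' code was present in 90% of A&Gs and a 'received' code in 25% to 50%, with a mean lag of 7 to 14 days. Prevalence was inflated by 1.9% to 7.1% per quarter and by 0.4% to 1.5% per year. A smaller opposite error also appears: a reply-only A&G is dropped when the patient has another request in the same period (0.1% to 0.2% of A&Gs by quarter, 0.4% to 0.7% by year). That lowers the event count, but not the number of patients counted in that period.

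**Reading B: the period is the whole window from 2015.** Nothing is double counted. But a request in 2023 removes the same patient's reply-only A&G from 2016. The loss depends on the share of A&Gs that are reply-only, which the protocol does not give. If 90% of A&Gs have a 'requested' code and 25% to 50% a 'received' code, independently, then 0.10 × 0.25 = 2.5% to 0.10 × 0.50 = 5% are reply-only. The simulation then lost 1.7% to 3.4% of recorded A&Gs, and annual prevalence was 1.5% to 2.9% too low. With only 70% 'requested' and 50% 'received' (0.30 × 0.50 = 15% reply-only), about 10% of A&Gs were lost and annual prevalence was about 8.6% too low.

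**Incidence.** Section 4.3 requires no A&G or referral code in the previous 24 months. Under reading A the earlier request lies inside that washout, so the stray reply does not become a new incident case.

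**The case against.** The strongest reply is that the only certain fault is an undefined phrase, and that de-duplicating a fallback code is detail an analysis plan commonly settles. WP1a is also described as descriptive and exploratory. Part of this stands. The protocol does not say that the period is a calendar period. A reader might take it so because section 4.3 works by year and quarter, but that is an inference. The two main harms, double counting and loss across years, also belong to different readings. Defining the phrase would not cure the rule, however. It would only choose which error occurs, because the rule as stated is per patient and per period on any reading.

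Second, section 4.2.8 explains that a code must be entered to save the e-RS activity, so A&Gs without a 'requested' code may be rare. That stands for reading B and would make its loss small. It does not help reading A, where the double count comes from A&Gs with both codes. If nearly all requests are coded, most replies admitted in a new period are duplicates.

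Third, a reader might infer that 1.74 A&Gs per person measures the loss under reading B. It shows only that repeat A&Gs occur. The loss turns on the unknown reply-only share.

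Fourth, a reader might infer a false time trend or false local differences. A constant lag and coding share would shift the level, not the slope. A false trend needs them to change, and the documents give no evidence on that. Sections 4.3.2 and 4.3.3 acknowledge that recording may have improved, and section 4.3 plans a descriptive comparison with published e-referral data. That is a check on trends, though it does not correct the rule.

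**Conclusion.** The point holds as a defect in a stated outcome definition. Section 4.2.8 links 'received' to 'requested' by patient and an undefined period, and each plausible reading miscounts.

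The size rests on assumed lags and coding shares. Under the year or quarter reading, quarterly counts and prevalence carry most of the error: 1.9% to 7.1% on prevalence under the simulated assumptions. Annual figures are probably little affected, at 0.4% to 1.5%, although even 1% (8 per 100,000) exceeds the planned sampling precision of ±5. Incidence is largely protected from double counting. Under the whole-window reading, the loss could be negligible or could reach several per cent, depending on how many A&Gs are reply-only.

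Two stronger conclusions are not supported. No stated sample-size or precision figure is wrong on this point. Nor does the rule misdate the 122-day windows in general: section 4.2.8 anchors them to the request date, and only reply-only A&Gs, which have no request date, must start from the reply. The matter should be settled before the series are produced, but it does not undermine WP1a as a whole.

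**What to change.** Replace the period test in section 4.2.8 with an episode rule:

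- A 'received' code within N days after a 'requested' code belongs to that request and is not counted. Any other 'received' code counts as an A&G.
- Set N from the observed distribution of request-to-reply gaps, and vary it in a sensitivity analysis.
- Apply the same rule to the annual, quarterly and 122-day analyses of WP1a, and to the A&G exposure in WP2.
- In the 122-day analyses, flag reply-only A&Gs or exclude them in a sensitivity analysis. The episode rule cannot recover their request date.

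The cost is a sentence or two in the protocol and a few lines of code. The downside is that a new, uncoded request made within N days of an earlier one is merged with it; varying N shows how much this matters.

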1.3 THEORETICAL FRAMEWORK

This study is underpinned by the pragmatist research paradigm. Accordingly, the study is problem centred and "real-world practice oriented" in asking "what works?" in relation to A&G to bring about change in quality care. We take a pluralist approach to answer research questions that require quantitative and qualitative lines of enquiry. Our mixed-methods evaluation has a sequential design with 4 work packages (WPs). WP1 is mixed-methods and will include a descriptive quantitative study using electronic healthcare records (EHR), specifically CPRD, and qualitative study using semi-structured in-depth PCC interviews to describe the use and experience of A&G, to identify tracer conditions and create a focus for WP2. WP2 will involve retrospective cohort studies, repeated for

NIHR 158681BADGER			
Protocol Version 2.0 18/06/2024	CPMS: 58336	IRAS No: 333799	CPRD ID: 24_004022

several tracer conditions. We will describe patient characteristics within the type of referral, with type of referral defined as A&G only; direct referral only; A&G and direct referral; no A&G and no direct referral. We will then observe the linked EHR to identify impact on quality and healthcare utilisation of A&G. WP3 runs in parallel to WP1 and WP2 and includes in-depth qualitative interviews with patients, SCSs, PCC and commissioners to understand their perspectives on the use of A&G. Interpretive description methodology¹⁹ will use clinical knowledge and the perceptions and experiences of participants to develop findings which can be applied to clinical practice, healthcare commissioning and policy development.

Reflexive thematic analysis will be used as the specific analytic strategy to identify these findings. Reflexive thematic analysis will be used allowing for familiarisation, coding, and generating and reviewing themes. Themes and subthemes will be generated iteratively by researchers independently according to commonality across the dataset, significance, and relevance to the research questions. Generated themes will be discussed with the PPIE group and stakeholders for their reflection.

WP4 uses results of WP1, WP2 and WP3 to co-design recommendations, as described below, to support best use of A&G in reducing compound pressures, whilst providing high quality care, and addressing any identified health inequalities.

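### Imputing A&G specialty from the codes most frequent within each specialty's direct referrals may systematically misallocate the specialty-specific A&G rates of WP1a aim 3

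*Protocol*

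**What the plan says.** WP1a aim 3 (Protocol 4.1) is to determine "which specialties and health conditions have higher rates of A&G". Section 4.3 carries this into the analysis: "Patterns of A&G use (number, prevalence, incidence) will also be described across specialties and type of health condition".

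The specialty variable is built in section 4.2.8:

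- A recorded specialty is used when there is one: "We will determine coded A&G events and, where possible, the specialty linked to the A&G".
- Otherwise the direct referrals are the source: "Given A&G coded events may not routinely have the specialty recorded we will use information from direct referrals". These are referrals with a named specialty, sampled from 2015, 2019 and 2023, with the morbidity and symptom codes recorded on the referral date or in the two weeks before.
- The key step is: "We will determine which Read or SNOMED CT codes are most frequently recorded with referral to each specialty". The team will then "use these to map (impute) specialties in those with an A&G event based on matching these codes" to those recorded around the A&G date.
- The fallback is limited: "Where the specialty is still unknown after this mapping exercise, we will review all codes" and agree a specialty by consensus, or leave it unknown.

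Type of health condition is taken either from specialty or from the morbidity or symptom code. Section 4.3.3 accepts that misclassification can occur, but takes it to be random and so of little consequence for bias. Section 1.3 uses WP1 "to identify tracer conditions and create a focus for WP2".

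**The concern.** The rule starts from the specialty and asks which codes are common in it. The task runs the other way: given the code seen at the A&G, which specialty was consulted? The answer to the second question depends on the volume of each specialty as well as on how common the code is within it. A code can be prominent among a small specialty's referrals although most patients with that code go to a large one. A general symptom code can be prominent in several specialties at once. Section 4.2.8 does not say how such a code is resolved, or what happens when an A&G has codes pointing to different specialties.

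A wrong match also goes unseen. Consensus review covers only events with no match, and section 4.2.8 states no comparison with A&G events whose specialty is recorded.

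At stake are the number, prevalence and incidence of A&G by specialty and, where health condition is derived from specialty, part of that breakdown too. Section 10.1.2 plans a report of this mapping by month 12 to support the work of integrated care boards. Errors of this kind would follow specialty size and code overlap, which does not fit the expectation of randomness in 4.3.3.

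**Working it through.** **Nothing to reproduce.** The protocol gives no code frequencies, specialty volumes, mapping accuracy or share of A&G events with a recorded specialty. All inputs below are assumed, to show the mechanism and its range.

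**Assumed inputs.** Code c occurs in 15% of referrals to a small specialty S and 5% of referrals to a large specialty L. L has k times the volume of S. All events without code c are allocated correctly, and A&G has the same specialty mix per code as direct referral.

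**Formula.** P(S | c) = n_S × P(c | S) / [n_S × P(c | S) + n_L × P(c | L)] = 0.15 / (0.15 + 0.05k).

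Rule 1 gives the code to the specialty with the higher P(code | specialty), which here is always S. Its error is 1 − P(S | c). Rule 2 gives the code wholly to the specialty with the higher P(specialty | code). Its error is the smaller of P(S | c) and 1 − P(S | c).

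| k | P(S given c) | Events with code c misallocated, rule 1 | Rule 2 |
|---|---|---|---|
| 1 | 0.75 | 25% | 25% |
| 2 | 0.60 | 40% | 40% |
| 5 | 0.375 | 62.5% | 37.5% |
| 10 | 0.23 | 77% | 23% |
| 20 | 0.13 | 87% | 13% |

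The two rules agree at similar volumes and part once L is large enough. For a code that belongs to one specialty only, they always agree.

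**Effect on counts at k = 10.** Take 1,000 events in S and 10,000 in L. Code c appears in 0.15 × 1,000 = 150 and 0.05 × 10,000 = 500 of them, 650 in all.

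- Rule 1: all 650 go to S. S = 1,000 + 500 = 1,500, or 1.50 times the truth. L = 9,500, or 0.95 times.
- Rule 2: all 650 go to L. S = 1,000 − 150 = 850, or 0.85 times the truth. L = 10,150, or 1.015 times.
- Proportional allocation: S receives 650 × 150/650 = 150 and L receives 500. Both totals are right.

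So the usual alternative of giving each code to its commonest specialty also distorts counts, in the opposite direction for S.

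**Does the direct-referral map carry over to A&G?** Keep k = 10 and the same code frequencies, and let the share of S relative to L in A&G be r times that in direct referrals. The odds are (0.15/0.05) × (1/10) × r = 0.3r.

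- r = 0.25: odds 0.075, P(S | c, A&G) = 0.07
- r = 1: odds 0.3, P = 0.23
- r = 4: odds 1.2, P = 0.55

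Proportional allocation is therefore right only if the specialty mix per code is shared. That can be checked only on A&G events with a recorded specialty.

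**The case against.** The strongest reply is that the sentence is loosely worded. It gives no list length, cut-off or tie-break, and it could mean a table of code by specialty in which each code goes to the specialty it most often accompanies. That would be modal P(specialty | code), not the wrong conditional. This reading is possible, and the protocol does not exclude it. It does not remove the problem: rule 2 above still distorts counts, shared codes are still given wholly to one side, and wrong matches still escape review.

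A second reply is that such detail belongs in an analysis plan, which is not shown. That would answer silence, but section 4.2.8 sets out a stepwise rule, and the point concerns that rule.

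A third is that the illustration rests on assumed inputs and that WP1a is descriptive. Both are true, and they limit how strongly the point can be put.

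Three stronger inferences are tempting and are not supported:

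- A reader might infer that a specialty where A&G has largely replaced referral is under-assigned by the stated rule because it supplies few records. Ranking within specialty ignores volume, so low volume alone does not cause this. That bias belongs to P(specialty | code) learned from direct referrals, which is why the fix needs a check on A&G data.
- A reader might object that A&G and direct referrals are compared by specialty with different instruments. Section 4.3 describes A&G across specialties and states no A&G-to-referral contrast by specialty.
- A reader might conclude that the tracer conditions for WP2 will be misdirected. Section 5.2.7 also draws on clinician interviews and on the public-involvement and stakeholder groups, so this is only possible.

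**Conclusion.** The concern holds in a limited form. As naturally read, section 4.2.8 does not use the probability of specialty given code. On either reading it leaves shared codes unresolved and sends only unmatched events to review. Specialty-specific A&G counts and rates under aim 3 may therefore be misallocated in a systematic way, and the statement in 4.3.3 that misclassification is random is not justified for imputed specialty.

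It would go too far to say that the rates will be wrong. Size and direction depend on code overlap, relative specialty volumes and the share of A&G events needing imputation, none of which the protocol gives. The factors of 1.50 and 0.85 rest wholly on the assumed 10:1 volumes and the 15% and 5% code frequencies. With codes specific to one specialty, the error from this source would be nil.

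A change is worth making because a named aim rests on this variable and the better method uses data already in hand.

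**What to change.** In section 4.2.8:

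1. Estimate P(specialty | code) from the sampled direct referrals, and allocate each A&G event without a recorded specialty across specialties in proportion to it, or by multiple imputation. Codes shared between specialties are then handled by construction.
2. On the A&G events that have a recorded specialty, report agreement between imputed and recorded specialty. Where numbers allow, recalibrate the probabilities, because the specialty mix of direct referrals may differ from that of A&G.
3. Report the recorded-specialty subset as a sensitivity analysis for aim 3.

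In section 4.3.3, qualify the statement that misclassification is random so that it does not cover imputed specialty.

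Imputing specialty for direct referrals in the same way is needed only if A&G and direct referral are later contrasted by specialty.

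The cost is some extra programming on data already extracted and a change of wording in two sections. The downside is that specialty counts become estimates with allocation uncertainty, which should be shown with them. The value of step 2 depends on how many A&G events carry a recorded specialty, which is not known from the protocol.
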